### **10.7 Handling of Multiplicity**

There will be no adjustment for multiple endpoints.

### **10.8 Efficacy Subgroup Analysis**

To evaluate the impact of various baseline characteristics on treatment effect, analyses will be performed for the primary efficacy variable of SVR12 using the following subgroups.

- HCV subtype (1a, 1b, or other)
- IL28B genotype (CC or non-CC)

- Race (black or non-black)
- Gender (male or female)
- Age < 65 yrs or ≥ 65 yrs)
- BMI (< 30 kg/m^2 or ≥ 30 kg/m^2)
- Type of response to HCV treatment in initial DAA combination study (treatment-naïve or treatment-experienced [null responder, partial responder, relapser])
- Baseline HCV RNA levels (< 800,000 or ≥ 800,000)
- Subjects with RBV dose modifications (yes or no)
- History of diabetes (yes or no)
- Baseline fibrosis score (F0 – F1, F2, F3 or F4)
- Achievement of eRVR (yes, no)
- Treatment in the initial DAA combination study

The number and percentage of subjects achieving SVR12 within each subgroup will be provided for all subgroups. If there are 2 or more subjects within the subgroup level, then two-sided 95% confidence intervals will be calculated using the Wilson score method.

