Subjects who complete TI treatment will continue on to Substudy 2, the PR Treatment Period, for continued dosing of pegIFN and RBV. Subjects who prematurely discontinue TI treatment may also continue on to Substudy 2, unless the investigator feels it is not appropriate to continue pegIFN and RBV either due to toxicity or to lack of virologic response. Substudy 2 will begin the day after the last dose of DAA. Substudy 2 is designed to allow completion of pegIFN + RBV treatment for a total duration of 48 weeks across Substudies 1 and 2 and to monitor HCV RNA levels and emergence of any ABT-450 and ABT-267 resistance-associated variants.

For subjects who complete Substudy 1, an additional 24 weeks of pegIFN and RBV will be administered in Substudy 2. Subjects who complete 24 weeks of treatment in Substudy 2 should undergo the procedures listed in the PR Final/PR Discontinuation Visit in [Table 5](#) (and [Table 6](#) for cirrhotic subjects), not the PR Week 24 visit and then continue on to Substudy 3.

Subjects who receive less than 24 weeks of TI treatment in Substudy 1 may receive pegIFN and RBV in Substudy 2 at the discretion of the investigator, up to a total of 48 weeks across Substudies 1 and 2. All subjects will continue to return to the site on an outpatient basis for the PR Treatment study procedures identified in [Table 5](#) (and [Table 6](#) for cirrhotic subjects). For those subjects who do not complete 24 weeks of TI treatment in Substudy 1, additional study visits as indicated in [Table 5](#) (and [Table 6](#) for cirrhotic subjects) should be performed if required to complete a total of 48 weeks across Substudies 1 and 2. These additional visits are PR Week 24, PR Week 36 and PR

Final/PR Discontinuation Visit (which may be out to 48 weeks or earlier). All subjects should complete the PR Final/PR Discontinuation Visit procedures at that subject's final visit in Substudy 2. In some cases this final visit may fall in between study visits listed in [Table 5](#). Sites should ensure that subjects adhere to the study visits listed in [Table 5](#) (and [Table 6](#) for cirrhotic subjects). Subjects who cannot complete their study visit per the visit schedule should ensure they do not run out of study drug prior to their next study visit. Compliance is critical to ensure adequate drug exposure.

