6.7.3 Management of Decreases in Hemoglobin

Reductions in hemoglobin are a well characterized side effect of ribavirin exposure. Hematologic abnormalities which the investigator believes are due to RBV therapy may be managed according to Table 12. Management will be different for subjects without a history of known cardiac disease and subjects with known cardiac disease.

If a subject experiences a hemoglobin decrease (as outlined in [Table 12](#)), a confirmatory test should be performed. If the hemoglobin decrease is confirmed, the management guidelines in [Table 12](#) should be followed.

Use of hematologic growth factors (e.g., epoetin, filgrastim) is permitted at the discretion of the investigator, only with approval of the AbbVie Study Designated Physician (see [Section 5.2.3.2](#) for further details). Management of hematologic growth factor therapy is the responsibility of the Investigator, and growth factors will not be provided by AbbVie.

Alternate management of hemoglobin decreases requires approval of the AbbVie Study Designated Physician.

Alternative management of the RBV dose in the setting of reduced renal function will also require approval of the AbbVie Study Designated Physician.

Table 12. Hematologic Toxicities

| Hemoglobin in Patients with No History of Cardiac Disease | |
|--|---|
| Hemoglobin < 10.0 g/dL, but ≥ 8.5 g/dL | Study drugs may be continued |
| | Reduce RBV dose to 600 mg/day and continue to monitor hemoglobin per protocol |
| | If hemoglobin increases to ≥ 10 g/dL, may increase RBV; with gradual dose increases in 200 mg increments towards original dose If Hb decreases to < 8.5 g/dL see appropriate row below |
| Hemoglobin < 8.5 g/dL | Permanently discontinue all study drugs Manage the subject as medically appropriate |
| | Enter discontinuation into appropriate eCRFs and create corresponding adverse event |
| | |
| Hemoglobin in Patients with History of Stable Cardiac Disease | |
| Hemoglobin decrease of ≥ 2 g/dL during a 4-week treatment period | Study drugs may be continued |
| | Reduce RBV dose to 600 mg/day and continue to monitor hemoglobin levels per protocol; manage subject as medically appropriate; AbbVie Study Designated Physician may be contacted |
| | If a subsequent hemoglobin result is greater than the level that triggered the dose reduction, the investigator may gradually increase RBV in 200 mg increments towards original dose |

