8.1 Statistical and Analytical Plans

8.1.1 Demographics

Demographics and baseline characteristics will be summarized overall, and based on treatment in the previous study. Demographics include age, weight, and body mass index (BMI), and the frequency of gender, race, ethnicity, age category (< 50 years and ≥ 50 years; < 65 years and ≥ 65 years), birth year (< 1945, 1945 to 1965, > 1965), BMI category (< 30 kg/m² and ≥ 30 kg/m²), and geographic region (North America, Europe, Australia/New Zealand, Latin America). Baseline characteristics will include HCV genotype/subtype (1a, 1b, other 1 subtype), IL 28B genotype (CC, CT, and TT; CC and non-CC), RBV dose modifications (yes, no), history of diabetes, history of bleeding disorders, baseline fibrosis score (equivalent to Metavir F0–F1, F2, F3–F4), prior response to pegIFN/RBV, type of response to combination DAA treatment in prior study, treatment during the gap between the prior study and Study M13-101 (none, pegIFN/RBV), baseline log₁₀ HCV RNA levels, baseline IP-10, baseline HOMA-IR, and tobacco and alcohol use status. Summary statistics (N, mean, median, SD, and range) will be generated for continuous variables (e.g., age and BMI). The number and percentage of subjects will be presented for categorical variables (e.g., gender and race).

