### **6.1 Definition of Baseline and Final Assessment**

#### **Definition of Baseline**

The baseline value refers to the last non-missing measurement collected before the first dose of study drug is received. All assessments on Study Day 1 should be performed prior to administering the first dose of study drug per protocol. The baseline value is therefore determined by the last non-missing measurement collected on or before the first day of study drug administration.

If multiple measurements are recorded on the same day, the last measurement recorded prior to dosing will be used as Baseline. If these multiple measurements occur at the same time or time is not available, then the average of these measurements (for continuous data) or the worst among these measurements (for categorical data) will be considered as the baseline value. This same baseline value will be used for the TI, PR, and PT Periods.

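### SAP 10.8 treats RBV dose modification and eRVR as baseline characteristics for SVR12, but both arise on treatment, and the RBV split can show a gap of either sign when dose has no effect

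*SAP*

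**What the plan says.** SAP 10.8 gives the purpose of its SVR12 subgroups as "To evaluate the impact of various baseline characteristics on treatment effect". Most of the list fits that purpose: HCV subtype, IL28B genotype, race, sex, fibrosis score and so on. Two entries do not: "Subjects with RBV dose modifications (yes or no" and "Achievement of eRVR (yes, no". Neither carries a time limit or a landmark. Each subgroup level gets a count and a percentage, with a 95% Wilson interval where it holds two or more subjects.

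SAP 6.1 defines baseline: "The baseline value refers to the last non-missing measurement collected before the first dose of study drug is received". RBV modification comes later than that. For a haemoglobin fall, Protocol 6.7.3 (Table 12) says "Reduce RBV dose to 600 mg/day and continue to monitor hemoglobin per protocol". Table 13 in 6.7.5 adjusts RBV for falling creatinine clearance, and 6.7 allows the dose to be lowered for other reasons. eRVR is HCV RNA below LLOQ at TI Weeks 4 through 12 (SAP 10.1).

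Protocol 8.1.1 also counts "RBV dose modifications (yes, no" among baseline characteristics. The SAP has partly moved away from this: 7.1 no longer lists RBV modification, and 8.0 reports it under disposition. SAP 12.1.1 does not record that change, and 10.8 keeps the variable in the baseline list.

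On duration, Protocol 5.1.3 says "Substudy 2 is designed to allow completion of pegIFN + RBV treatment for a total duration of 48 weeks across Substudies 1 and 2". Protocol 5.4.1.1 stops all study drugs for failure at TI Week 12, for failure at TI Week 24, and on confirmed rise or breakthrough. After a Week 4 failure only the DAAs must stop.

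**The concern.** A yes/no variable that can become yes at any time on RBV is more likely to be yes in subjects who stay on RBV longer. Time on RBV here depends partly on the outcome, because several virologic failure rules end all study drugs while completers have 48 weeks. This is immortal-time bias: early virologic failures tend to collect in the no-modification group whether or not RBV dose matters.

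eRVR has a related fault. It is an early reading of the same virologic response that SVR12 measures later, so it can predict SVR12 on treatment but cannot be a baseline modifier of it. A subject still missing HCV RNA at TI Week 4 or Week 12 after imputation counts as an eRVR failure (SAP 10.3), so some early stoppers may fall in the no group for that reason alone.

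At stake is how a reader uses the table. Under a heading that promises the impact of baseline characteristics, a gap between the RBV rows invites a conclusion about dose reduction that the comparison cannot support.

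**Working it through.** The documents give no figure for this point, so there is nothing to reproduce. The check asks what the planned table shows when RBV modification has no effect on SVR12.

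**Inputs**
- From the documents: 48 weeks of RBV for completers (Protocol 5.1.3); all-drug stops at TI Weeks 12 and 24 (Protocol 5.4.1.1); up to 35 subjects (Protocol synopsis).
- Assumed, because the documents give no values: 40% of completers have a modification by Week 48; completers' SVR12 is 85%; 25% of subjects stop early, at Week 12, and do not reach SVR12; modification occurs at a constant rate while on RBV.

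**Step 1. Chance of modification by week t.** P(t) = 1 - 0.60^(t/48). P(48) = 0.40, P(24) = 0.225, P(12) = 0.120.

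**Step 2. SVR12 in each group, early stops at Week 12.**
- Modified: 0.75 × 0.40 × 0.85 / (0.75 × 0.40 + 0.25 × 0.120) = 0.255 / 0.330 = 77.3%.
- Not modified: 0.75 × 0.60 × 0.85 / (0.75 × 0.60 + 0.25 × 0.880) = 0.3825 / 0.670 = 57.1%.
- Gap: +20.2 points with no true effect. With stops at Week 24, P(24) replaces P(12) and the groups are 71.6% and 59.4%, a gap of +12.1.

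**Step 3. What fixes the sign.** The gap is zero when early stoppers and completers have the same proportion modified, and changes sign beyond that. Protocol Table 12 has a route that raises the early stoppers' proportion: RBV is reduced at one haemoglobin level and all drugs are stopped at a lower one. For subjects with cardiac disease, one stop applies after 4 weeks at the reduced dose. Let q be the share of early stops that follow a modification in this way, so that the early stoppers' proportion modified is q + (1 - q) × 0.120.

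| q | Modified | Not modified | Gap (points) |
|---|---|---|---|
| 0 | 77.3% | 57.1% | +20.2 |
| 0.25 | 66.2% | 62.2% | +4.0 |
| 0.32 | 63.8% | 63.8% | 0 |
| 0.50 | 58.0% | 68.3% | -10.3 |

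The zero point solves q + (1 - q) × 0.120 = 0.40, so q = 0.280 / 0.880 = 0.32.

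**Step 4. Timing of modifications.** If all modifications come in the first 12 weeks, then P(12) = P(48) = 0.40 and the gap is zero for any stop at Week 12 or later.

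**Step 5. Other inputs.** With completers' SVR12 at 90%, 20% stopping at Week 12 and 40% modified, the groups are 83.7% and 65.9%, a gap of +17.9. It becomes -9.4 when half of early stops follow a modification. With no early stopping, both groups show the same SVR12, so the gap comes only from unequal time at risk.

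**Step 6. Precision at N = 35.** In the Step 2 scenario about 12 of 35 subjects are modified (0.330 × 35 = 11.5). Wilson 95% intervals are 47 to 91% for 9/12 and 37 to 74% for 13/23. They are wide and overlap. They express sampling error only.

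**The case against.** The strongest reply is that this is one lead-in phrase in a descriptive table. SAP 10.1 makes no statistical comparisons, the study has one arm and up to 35 subjects, and neither document has an objective about reducing RBV. SAP 7.1 has already dropped RBV modification from the baseline summary. All of this is correct and limits the severity. It does not settle the matter, because 10.8 itself states an aim of evaluating impact and places both variables under it.

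A reader might infer that the table must favour dose reduction. The documents do not support that:
- Toxicity stops after a reduction (Protocol Table 12) pull the other way.
- Week 4 failures may continue RBV at the investigator's discretion, and subjects with a confirmed rise or breakthrough may stay on treatment with approval of the sponsor's Study Designated Physician (Protocol 5.4.1.1).
- The synopsis extends the discretion to continue pegIFN/RBV to any subject meeting stopping criteria during DAA treatment, while 5.4.1.1 stops all drugs at Weeks 12 and 24. These passages must be reconciled, and how many failures have shortened RBV exposure depends on it.

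The objection that a Week 12 landmark would be thin also stands. Under the constant-rate assumption it would hold about 3 modified subjects among 26 (35 × 0.75 = 26; 26 × 0.120 = 3). It would also leave out anyone who failed before Week 12. It can only be supportive. Finally, that modification is counted over all 48 weeks is an inference, since 10.8 states no period.

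**Conclusion.** The point holds as a minor one. RBV dose modification and eRVR are post-baseline under the SAP's own definition and do not belong among baseline characteristics. For RBV, unequal time at risk alone can produce a gap of about +20 points, none, or about -10 points when dose has no effect. Which of these applies depends on why and when subjects stop and when modifications occur. The 40%, 85% and 25% inputs and the constant rate are assumptions, so these figures show what is possible and do not predict the result.

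Two stronger readings should be resisted: that the bias always favours modification, and that the efficacy result is compromised. The first fails on the toxicity and continuation routes above. The second fails because the primary SVR12 estimate uses all treated subjects and does not involve this split.

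**What to change.** In SAP 10.8, remove RBV dose modification and eRVR from the baseline subgroup list. Report them under a separate heading for on-treatment (post-baseline) factors, descriptive only. For the two RBV groups, show RBV duration and time of first modification, and state that the split does not measure the impact of dose modification on SVR12.

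Optionally, add a supportive landmark table among subjects still on RBV at TI Week 12, classified by modification up to that visit. It drops early stoppers, ignores later reductions and may have very few modified subjects.

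Record in SAP 12.1.1 that RBV modification is no longer treated as the baseline characteristic listed in Protocol 8.1.1. No protocol amendment is needed. The cost is SAP wording and a few added rows, plus one table if the landmark is included. RBV start and stop dates and dose modifications are already recorded in the eCRF, so no new data are collected.

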5.1.1 Pre-screening

Subjects who receive at least 1 dose of DAA and who experience virologic failure either during DAA therapy (rebound, breakthrough or failure to suppress) or after the end of therapy (relapse) in a previous AbbVie/Abbott DAA combination study, will be offered enrollment in this study if the subject meets all of the eligibility criteria specified in Section 5.2.1 and Section 5.2.2, and if study drug therapy is considered medically appropriate based on the opinion of the investigator.

[figure not shown]
The Pre-screening Visit may be conducted at any time after the subject is confirmed failure from the previous AbbVie/Abbott DAA combination study. Once the subject is confirmed to meet all the eligibility criteria then the subject must discontinue from the previous AbbVie/Abbott DAA combination study. Subjects must provide written (signed and dated) informed consent for Study M13-101 prior to any study-specific procedures, including the population sequencing analysis done at the Pre-screening Visit. The investigator will record the details of the informed consent process in the subject's medical records. A blood sample will be collected for all subjects at the Pre-screening Visit for population sequencing of the HCV NS3/4A protease and NS5A genes. Another sample will be drawn at the same time at this visit to determine the HCV RNA level. The HCV RNA level must be at least 2000 IU/mL in order to perform the population sequencing testing. The Pre-screening Visit may be repeated at a later date per the investigator's discretion if the HCV RNA level is < 2000 IU/mL. Subjects will retain their subject number from the previous DAA combination study. This information will be entered into the Interactive Response Technology (IRT) system under the Pre-screening Visit flow. This number will be written on the Pre-screening Visit blood collection tubes and on the lab requisition form prior to shipping the samples to the central laboratory. The results of the population sequencing will take approximately 3 weeks to complete.

Among subjects who previously experienced null or partial response to pegIFN/RBV treatment at any time prior to pre-screening for this study, or who had any prior failure with pegIFN/RBV plus telaprevir in the previous AbbVie/Abbott study, enrollment will be limited to only those subjects in whom variants in HCV NS3/4A protease and NS5A at

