5.2.3.1 Prior HCV Therapy

Any HCV therapy the subject received after terminating from the previous AbbVie/Abbott DAA combination study and prior to enrollment in this study must be recorded. Use of any investigational anti-HCV agents or approved DAAs during this period excludes a subject from this study. Subjects who received pegIFN and RBV during this period may be enrolled in the study. These subjects should have complete documentation of pegIFN and RBV treatment history, including start and stop dates, type of response (if known), and reason for discontinuation. Categories on the eCRF will include the following:

- **Null responder:** Subject has documentation that they previously received PegIFN/RBV for at least 10 weeks and failed to achieve a $2 \log_{10}$ IU/mL HCV RNA decrease at Week 12 (Week 10 to Week 16)
- **Partial responder:** Received at least 20 weeks of PegIFN/RBV for the treatment of HCV and achieved $\geq 2 \log_{10}$ reduction in HCV RNA at Week 12 (Weeks 10 – 16), but failed to achieve HCV RNA undetectable at the end of treatment
- **Relapser:** Received at least 36 weeks of PegIFN/RBV for the treatment of HCV and was undetectable at the end of treatment, but HCV RNA was detectable within 52 weeks of treatment follow-up
- **Not documented/Other**

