## **7.0 Demographics, Baseline Characteristics, Medical History, and Previous/Concomitant Medications**

### **7.1 Demographic and Baseline Characteristics**

Demographics and baseline characteristics will be summarized for the Safety Population.

Demographics include age, weight, and body mass index (BMI) as continuous variables, and gender, race ethnicity, age category (< 50 years and ≥ 50 years; < 65 years and ≥ 65 years), birth year (< 1945, 1945 to 1965, > 1965), BMI category (< 30 kg/m^2 and ≥ 30 kg/m^2), and geographic region (North America, Europe, Australia/New Zealand, Latin America ), original study as categorical variables. Baseline characteristics will include HCV genotype/subtype (1a, 1b, other 1 subtype), IL 28B genotype (CC, CT, and TT; CC and non-CC), initial DAA combination study prior to Study M13-101, treatment

status at entry to initial DAA combination study prior to Study M13-101 (treatment naïve or treatment experienced [null responder, partial responder or relapser]), type of response to HCV treatment in initial DAA combination study (null responder, partial responder, relapser), treatment in the initial DAA combination study, baseline  $\log_{10}$  HCV RNA levels (continuous), history of diabetes, baseline fibrosis score (F0 – F1, F2, F3, F4), baseline HCV RNA levels ( $< 800,000$  IU/mL or  $\geq 800,000$  IU/mL), baseline IP-10 ( $< 600$  ng/L or  $\geq 600$  ng/L) and baseline HOMA-IR (fasting glucose [MMOL/L]  $\times$  fasting insulin [MCIU/ML]/22.5,  $< 3$  mU  $\times$  mmol/L or  $\geq 3$  mU  $\times$  mmol/L). Subjects who do not have a fasting glucose and fasting insulin value at Baseline will be excluded from the summary of baseline HOMA-IR.

Summary statistics (N, mean, median, SD, and range) will be generated for continuous variables (e.g., age and BMI). The number and percentage of subjects will be presented for categorical variables (e.g., gender and race). Summary statistics for baseline weight will be computed overall and separately by gender.

IL28B rs12979860 genotype was resulted as C/C, C/T, T/T, or Unable to Assign Genotype by the central laboratory or Abbott/AbbVie Pharmacogenetics group in the initial DAA combination study.

History of diabetes is defined as presence of "Metabolic/Diabetes mellitus" on the MH eCRF.

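### The SAP 10.8 row labelled as response in the initial DAA study carries the levels of pre-DAA treatment history, and the matching SAP 7.1 variable has no level for on-treatment breakthrough or rebound

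*SAP*

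**What the plan says.** **Protocol.** Section 8.1.1 lists two separate baseline factors: "prior response to pegIFN/RBV, type of response to combination DAA treatment in prior study". Section 5.1.1 describes the qualifying event as "virologic failure either during DAA therapy (rebound, breakthrough or failure to suppress) or after the end of therapy (relapse"). Section 5.2.3.1, repeated in 5.4.2, defines null responder, partial responder and relapser for pegIFN/RBV courses; a null responder, for example, is someone who "previously received PegIFN/RBV for at least 10 weeks" without the required early fall in HCV RNA.

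**SAP 7.1.** Two baseline variables appear one after the other. The first is treatment "status at entry to initial DAA combination study prior to Study M13-101 (treatment naïve or treatment experienced [null responder, partial responder or relapser"]). The second is "type of response to HCV treatment in initial DAA combination study (null responder, partial responder, relapser").

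**SAP 10.8.** One SVR12 subgroup row is labelled "Type of response to HCV treatment in initial DAA combination study", with the levels "treatment-naïve or treatment-experienced [null responder, partial responder, relapser"]. A separate row covers the treatment given in the initial study, which is the regimen and not the mode of failure.

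**SAP 12.** The list of changes from the protocol includes several edits to baseline characteristics and efficacy summaries. It mentions none to this variable.

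**The concern.** This trial retreats people in whom a DAA combination failed, so how that combination failed is a natural descriptor of the population. Protocol 5.6.3 names the failure category in the previous study among the factors weighed when deciding on enrolment.

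The SAP gives one variable name two sets of levels. A programmer who follows the levels in 10.8 will tabulate SVR12 by treatment history before the DAA study, under a heading that says response in it. A programmer who follows the label will go to 7.1 and find no level for a subject whose virus broke through on treatment. The word relapser is also left open: under the first 7.1 variable it means relapse before the initial DAA study, and under the second it could mean relapse after the DAAs.

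At stake are one baseline row and one subgroup row of the report.

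**Working it through.** The plan gives no figure on this point, so the main check is a comparison of definitions. Arithmetic is needed only for the size.

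**Step 1. Match levels to labels.**

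| Place | Label (paraphrased) | Levels |
|---|---|---|
| SAP 7.1, first variable | Status at entry to initial DAA study | naïve; null; partial; relapser |
| SAP 7.1, second variable | Response in initial DAA study | null; partial; relapser |
| SAP 10.8 row | Response in initial DAA study | naïve; null; partial; relapser |
| Protocol 5.1.1 | Failure in previous DAA study | rebound, breakthrough or failure to suppress on treatment; relapse |

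The 10.8 levels match the first 7.1 variable one for one. The 10.8 label is that of the second.

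**Step 2. Can the 10.8 levels describe a response in the initial study?** Protocol 5.1.1 and inclusion criterion 3 require at least one DAA dose and virologic failure in that study. The naïve level is therefore impossible as a response there and makes sense only as status at entry.

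**Step 3. Can the levels of the second 7.1 variable describe DAA failure?** The documents define null, partial and relapser only for pegIFN/RBV courses of at least 10, 20 and 36 weeks. SAP 4.2 calls the earlier study pegIFN-free. Read loosely, relapser covers DAA relapse, and null or partial might be stretched to failure to suppress. Nothing covers breakthrough or rebound. A possible exception is the group given pegIFN/RBV plus telaprevir in a previous study, capped at ten by protocol 5.2, who might fit the pegIFN/RBV categories.

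**Step 4. Size.** Protocol 3.0 states the mode of failure for these Phase 3 subjects:

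| Study | On-treatment | Relapse |
|---|---|---|
| M11-646 (1a and 1b) | 1 + 0 = 1 | 6 + 1 = 7 |
| M13-098 | 0 | 5 + 2 = 7 |
| M13-961 | 1 | none stated |
| M14-002 (with and without RBV) | 1 + 6 = 7 | 1 + 10 = 11 |
| M13-099 (12 and 24 weeks) | 1 + 3 = 4 | 12 + 1 = 13 |
| Total | 13 | 38 |

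M13-389 had no failures. The on-treatment share is 13 / (13 + 38) = 13/51 = 25%. Applied to 35 subjects, 35 × 13/51 = 8.9, or about 9.

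The share varies by study: 0/7 in M13-098, 1/8 (13%) in M11-646, 4/17 (24%) in M13-099 and 7/18 (39%) in M14-002, with a single on-treatment failure in M13-961. Leaving out M13-961, the range applied to 35 runs from 0 to 35 × 7/18 = 13.6, or about 14. The documents do not split on-treatment failures into breakthrough and failure to suppress, so the number with no level even on a loose reading could be smaller than 9.

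**The case against.** The strongest reply is that this is a labelling slip in one of 13 descriptive subgroup rows, in a plan that makes no statistical comparisons. The levels would be printed in the table, and a reader who sees naïve and experienced is unlikely to take them for breakthrough and relapse. That lowers the risk of misreading, but it leaves the label wrong and the second 7.1 variable incomplete.

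Four stronger readings are tempting, and the documents do not support them.

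- *SVR12 by mode of DAA failure cannot be reported.* It is not reportable from the SAP as specified. Protocol 5.6.3 treats the failure category as known when enrolment is decided, so the levels can be redefined.
- *The SAP breaks a protocol commitment to that analysis.* Protocol 8.1.1 requires type of DAA response only as a baseline characteristic. Protocol 8.1.3 plans the primary and secondary endpoints overall and by previous treatment group, and the covariates in 8.1.4 do not include mode of DAA failure. Only the SAP's own row label implies such an analysis.
- *Treatment history before the DAA study has no row of its own.* SAP 7.1 already has one. The fault is that 10.8 attached its levels to another label.
- *Every subject is misclassified at baseline.* Relapser, under a label naming the initial DAA study, can reasonably be read as DAA relapse, and 38 of the 51 Phase 3 failures were relapses. The clear gap is for on-treatment breakthrough or rebound.

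One caution about cost also stands. Inclusion criterion 3 shows that failure was established, but not that its type is held in this trial's database. SAP 7.2 describes the transfer of medical history only.

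**Conclusion.** The point holds as a mismatch between label and levels in SAP 10.8 and a missing level in SAP 7.1. As written, the SVR12 row shows treatment history before the DAA study under a DAA-response label, and on-treatment breakthroughs in the initial study have no valid baseline level.

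The estimate of about 9 of 35 assumes that the enrolled mix resembles the pooled Phase 3 failures and that all 35 places are filled. Neither is established: 35 is a ceiling in the synopsis, earlier-phase studies may contribute subjects, and protocol exclusion criterion 1 removes some failures with listed variants. The conclusion about the definitions does not depend on that figure.

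The primary SVR12 estimate, the secondary estimates and the safety analyses are unaffected. The sponsor should correct this before the tables are programmed, but it does not threaten the trial's main result.

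**What to change.** 1. **SAP 7.1.** Keep the treatment-status-at-entry variable. Change the levels of the initial-DAA-study response variable to on-treatment virologic failure (breakthrough or rebound, or failure to suppress) and relapse, taken from the initial study's own failure classification.
2. **SAP 10.8.** Replace the single row with two: (a) treatment status at entry to the initial DAA study, with its present levels; (b) type of virologic failure in the initial DAA study, with the new levels. Report SVR12 and the planned 95% Wilson interval for each level, under the existing rule of at least 2 subjects per level.
3. **SAP 12.** Record the change.

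The cost is SAP wording, table shells and one more descriptive subgroup row with small cells. If the type of failure is not already in this trial's database, it will have to be drawn from the initial studies' data.
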